2.2 Trial Flow Chart

Study Procedures	Screening	Baseline	Treatment Phase						Follow-Up	Unscheduled
	Visit 1	Visit 2	Visit 3	Visit 4	Visit 5	Visit 6	Visit 7	Visit 8	Visit 9	U ^w
Day Relative to First Dose of Study Drug	Days -7 to -1	Day 1	Day 3 (± 1 day)	Week 1 [Day 4 to 8]	Week 2 [Day 9 to 15]	Week 4 [Day 16 to 29]	Week 6 [Day 30 to 54]	Week 12 / EOT ^a [Day 84 (±4 weeks)]	30 Days Posttherapy (±2 weeks)	Unscheduled
Informed Consent/assent	X									
Review Inclusion/Exclusion Criteria	X	X								
Issue Subject Identification Card	X									
Collect Subject Identification Card									X	
Medical/Disease History	X									
Pharmacogenetics Sampling (optional) ^b		X								
Stratification and Randomization by IVRS		X								
Problem Focused Physical Examination	X	X		X	X	X	X	X	X	X
Weight	X									
Vital Signs ^c	X	X	X	X	X	X	X	X	X	X
Recording of Previous Treatments ^d	X	X								
Assessment of Clinical Signs and Symptoms of Invasive Aspergillosis	X	X	X	X	X	X	X	X	X	X
Electrocardiogram (ECG) ^z	X	X ^e	X	X				X ^f		X
Hematology ^g	X	X	X	X	X	X	X	X	X	X
Serum Chemistry ^h	X	X	X	X	X	X	X	X	X	X
Serum hCG Pregnancy Test ⁱ	X									X

Study Procedures	Screening	Baseline	Treatment Phase						Follow-Up	Unscheduled
	Visit 1	Visit 2	Visit 3	Visit 4	Visit 5	Visit 6	Visit 7	Visit 8	Visit 9	U ^w
Day Relative to First Dose of Study Drug	Days -7 to -1	Day 1	Day 3 (± 1 day)	Week 1 [Day 4 to 8]	Week 2 [Day 9 to 15]	Week 4 [Day 16 to 29]	Week 6 [Day 30 to 54]	Week 12 / EOT ^a [Day 84 (±4 weeks)]	30 Days Posttherapy (±2 weeks)	Unscheduled
Serum for Aspergillus Galactomannan EIA ^{i, x}	X	X	X	X	X	X	X	X	X	X
Serum for Beta-D-Glucan Assay ^j	X	X	X	X	X	X	X	X	X	X
Mycology Testing ^k	X	X		X	X	X	X	X		X
Blood for CYP 2C19 genotyping ^l		X								
Diagnostic Imaging ^{m, x}	X	X ⁿ			X ⁿ	X ⁿ	X ^o	X	X ^p	X
Study Drug Dosing ^q		X	X	X	X	X	X	X		X
Concomitant Treatments ^r		X	X	X	X	X	X	X	X	X
Assess Global Clinical Response							X ^t	X		
Plasma Pharmacokinetic Assessment ^s		X		X	X	X	X	X		X
Collect Unused Medications			X	X	X	X	X	X		X
Study Medication Diary/ Dosing Compliance Assessment ^y			X	X	X	X	X	X		X
Drug Accountability Inventory			X	X	X	X	X	X		X
Safety (Adverse Events) Evaluation	X	X	X	X	X	X	X	X	X	X
I / IFI Assessment ^u							X	X	X	
Mortality Assessment ^u			X	X	X	X	X	X	X	X

Study Procedures	Screening	Baseline	Treatment Phase						Follow-Up	Unscheduled
Visit Number	Visit 1	Visit 2	Visit 3	Visit 4	Visit 5	Visit 6	Visit 7	Visit 8	Visit 9	U ^W

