Prophylaxis of IFI with azole or polyene antifungal drugs. This includes itraconazole, posaconazole, voriconazole, isavuconazole, inhaled or systemic amphotericin or lipid-associated amphotericin)	Discontinue at randomization
Nasal sprays of amphotericin B and aerosolized amphotericin B	Discontinue at randomization

Prohibited Medications Prior to Start of Study Treatment and During Study Treatment	Washout Period^a
Medications that are known to interact with azoles and may lead to life-threatening side effects: astemizole, cisapride, ebastine, halofantrine, pimoziide, quinidine, and terfenadine.	10 days (astemizole) 24 hours (others)
Ergot alkaloids (ergotamine, dihydroergotamine or other licensed or investigational members of this class).	2 days
Medications that are known to result in a false positive galactomannan EIA result: amoxicillin/clavulanate, and Plasma-Lyte. ^e	Prohibited during screening phase
Medications known to lower the serum concentration/efficacy of azole antifungals: barbiturates, carbamazepine, cimetidine, isoniazid, phenytoin, rifabutin, rifampin, and St. John's Wort (hypericum perforatum).	24 hours
HMG-CoA reductase inhibitors metabolized via CYP3A4 (e.g., simvastatin, lovastatin, and atorvastatin).	24 hours
Cyclophosphamide ^{b, d}	24 hours
Fosamprenavir, Ritonavir and efavirenz	24 hours
Vinca Alkaloids ^d	24 hours
Sirolimus	7 days

^a These waiting times should be observed prior to start of study treatment and during study treatment in subjects receiving a prohibited drug as prior therapy or should be observed after study drug is stopped before the prohibited medication is prescribed. No concurrent use is permitted. Deviations from these washout periods must be approved by the sponsor prior to use of study drug or prohibited agent.

^b Low dose cyclophosphamide use is allowed during the treatment period with a temporary interruption of study therapy on the day of cyclophosphamide dosing.

^c Investigational use of MK-8228 will require a 14-day washout period (rather than 30 days)

^d Concomitant use of Cyclophosphamide and vinca alkaloids is prohibited on study therapy. Subjects can remain on study if use of cyclophosphamide or vinca alkaloids therapies is needed but a washout of study drug for 24 hours must occur.

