7.4.2 Non-Trial Treatments

7.4.2.1 Prior and Concomitant Medications

7.4.2.1.1 Medications, Supplements, and Other Substances Prohibited Prior to Randomization and During the Trial

A record of all prior medication (prescription or over the counter) taken by the subject within 7 days before starting the study and all concomitant therapy taken by the subject during the study is to be obtained and recorded in the subject's eCRF. Parenteral nutrition products will also be documented as concomitant therapy. A record of chemotherapeutic agents used for any chemotherapy regimen within 30 days of Enrollment is to be obtained. A record of all prior immunosuppressive therapies and antifungal therapy should be recorded for 30 days prior to Baseline through Day 1. The identity of the therapy, route, and regimen, the dates started and stopped (or notation of "continuing" if that is the case), and the reason for use are to be included in the record.

Nasal sprays of amphotericin B (AMB) and aerosolized AMB are prohibited during the Treatment Phase. If subjects are on such treatment before study entry, such drugs must be discontinued at the time of Enrollment. Investigational drugs (i.e., other drugs not yet approved for marketing by the FDA or local health authorities) are also prohibited during the Treatment Phase.

Topical nonabsorbable antifungals may be used for the treatment of oropharyngeal candidiasis, vaginal candidiasis, or cutaneous fungal infection. These include: oral AMB, miconazole (oral or topical), nystatin (oral or topical), oral or topical clotrimazole. All other topical, nonabsorbable antifungal therapies must be approved by the sponsor prior to use. No other topical or oral antifungal agents may be used as prophylactic treatments (e.g., clotrimazole as prophylaxis in patients with mucositis).

The medications, supplements, and other substances prohibited prior to and after randomization are listed in [Table 2](#) in Section 7.3.2 with the subject exclusion criteria.

The washout period for study medication after discontinuation is approximately 7 days. Subjects should be monitored for untoward reactions if any of the prohibited medications are administered during the washout period (7 days post treatment) and AEs related to potential drug interactions should be recorded in the subject's eCRF.

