7.4.2.2 Other Treatments

Clinical and/or QTc monitoring is recommended when the study drug is coadministered with one of the following drugs that have reported a potential risk of torsades de pointes: amiodarone, chlorpromazine, clarithromycin, domperidone, droperidol, levomethadyl, mesoridazine, methadone, erythromycin, sparfloxacin, and thioridazine.

In addition to the medications in [Table 8](#), the drugs listed below are permitted, although their efficacy and safety should be clinically monitored and/or serum levels followed with appropriate dosage adjustments as necessary at the initiation of study drug, periodically during treatment, and after discontinuation of study drug:

- Oral hypoglycemic agents
- Digoxin
- Coumadin-type anticoagulants
- Calcium channel blockers
- Theophylline
- Antiretroviral therapy (e.g., atazanavir, or tenofovir).

POS interferes with the hepatic clearance of triazolam and midazolam, and thus, may enhance the sedative effects of these agents. Therefore, these agents are not allowed unless monitoring is provided for excessive sedation.

Please refer to POS and VOR product circulars for the most up to date details regarding the drugs and any updates in contraindications.

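### Table 2 reuses pre-treatment waits after study drug stops, so three groups of interacting drugs may start 5 to 6 days before the plan's own 7-day washout ends

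*Combined protocol and SAP*

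**What the plan says.** Table 2 in Section 7.3.2 has a single washout column. Footnote a says that these times apply before and during study treatment for a subject who was taking a prohibited drug, and that in the reverse direction they "should be observed after study drug is stopped before the prohibited medication is prescribed". The same footnote rules out concurrent use and requires sponsor approval for any departure from the waits.

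Three rows matter here:

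- "Medications that are known to interact with azoles and may lead to life-threatening side effects": seven named drugs, with a wait of "10 days (astemizole) 24 hours (others"). The six at 24 hours are terfenadine, quinidine, pimozide, halofantrine, ebastine and cisapride.
- "Ergot alkaloids (ergotamine, dihydroergotamine or other licensed or investigational members of this class"): 2 days.
- Statins metabolized by CYP3A4, with atorvastatin, lovastatin and simvastatin as examples: 24 hours.

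Section 7.4.2.1.1 states: "The washout period for study medication after discontinuation is approximately 7 days". It continues: "Subjects should be monitored for untoward reactions if any of the prohibited medications are administered during the washout period (7 days post treatment"), with adverse events from potential interactions to be recorded. It then points to Section 7.4.2.1.2, which calls posaconazole (POS) a potent CYP3A4 inhibitor and advises caution, possible dose reduction and close monitoring when CYP3A4 substrates are given with it. Section 7.4.2.2 adds: "Please refer to POS and VOR product circulars for the most up to date details regarding the drugs and any updates in contraindications". Section 7.2 follows serious adverse events to 30 days after the last dose.

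**The concern.** A wait before study drug starts lets the prohibited drug clear. A wait after study drug stops lets the azole clear. One number need not suit both purposes, and the life-threatening-interaction row suggests that here it does not: after stopping, all seven drugs meet the same residual azole, yet astemizole waits 10 days and the rest 24 hours. Azole clearance cannot explain that difference.

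Study drug is blinded (Section 7.4.1.4), so the prescriber does not know which azole is clearing, and one wait has to serve for either. A plausible case is a subject taken off a CYP3A4 statin to enter the trial and put back on it when therapy ends. Table 2 allows that the next day. What is at stake is an avoidable interaction in the week after the last dose. Efficacy estimation, sample size and power are not involved.

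**Working it through.** No power or error-rate calculation applies, and the plan's 7 days cannot be reproduced because the documents give no half-life for either azole. The check compares the waits in Table 2 with the washout in Section 7.4.2.1.1.

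**Shortfall against 7 days (168 hours).**

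| Row | Wait after stopping | Share of washout | Shortfall |
|---|---|---|---|
| Six life-threatening-interaction drugs | 24 h | 24/168 = 14% | 7 − 1 = 6 days |
| CYP3A4 statins | 24 h | 14% | 6 days |
| Ergot alkaloids | 48 h | 48/168 = 29% | 7 − 2 = 5 days |
| Astemizole | 240 h | 143% | none |
| Sirolimus | 168 h | 100% | none |

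The contrast within the life-threatening-interaction row is 240/24 = 10-fold.

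**How many rows are affected.** Table 2 has 14 rows, of which 9 state a wait in hours or days. Of those, 7 contain a wait under 7 days: the three at issue, plus drugs that lower azole levels, cyclophosphamide, vinca alkaloids, and the fosamprenavir/ritonavir/efavirenz row. The azole-lowering row is listed for its effect on the azole, so it does not matter once study drug has stopped. The other three are taken up under the objection.

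**Visits in the washout week.** Visit 9 in the flow chart (Section 2.2) is headed "30 Days Posttherapy (±2 weeks"), so it falls 30 − 14 = 16 to 30 + 14 = 44 days after therapy. For a subject whose last dose and end-of-therapy visit are both on Day 84, washout ends about Day 84 + 7 = 91, and Visit 9 falls between Day 84 + 16 = 100 and Day 84 + 44 = 128. No scheduled visit lies in the washout week for that subject. The result does not carry over to everyone. The end-of-therapy window is ±4 weeks, early discontinuers are still expected at later scheduled visits (Sections 7.2 and 7.3.3), and unscheduled visits are possible.

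**Illustration only.** Assume first-order elimination and that 7 days equals k half-lives. The fraction remaining at t hours is then 0.5^(t·k/168). For k = 3, 5 and 7 this gives 74%, 61% and 50% at 24 hours, and 55%, 37% and 25% at 48 hours. The documents do not state k, and the conclusion does not depend on it.

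**The case against.** The strongest reply is that the sponsor saw the overlap and made a choice. The sentence giving the 7-day washout is followed directly by the rule for prohibited drugs given inside it, which is to monitor and record. Together with the caution and dose-adjustment text in 7.4.2.1.2, which bears on the statin example, the circular referral and the 30-day follow-up for serious events, this is real mitigation. A reader might infer that the week after stopping is unguarded, or that the plan breaches its own safety limit. Neither follows: 7 days is given as a washout figure, and nowhere as the minimum for safe co-prescription. What stands against the reply is that each measure acts on or after exposure, or points elsewhere, while footnote a gives the site a specific number of 24 hours or 2 days.

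A second reply is that footnote d accepts 24 hours off study drug for cyclophosphamide and vinca alkaloids, so the plan does not treat 24 hours as too short in general. That rule is for subjects who stay on study and need chemotherapy. It does not explain restarting a statin or an ergot, or starting a drug from the life-threatening-interaction row, the day or two after permanent discontinuation. It is a fair criticism that leaving the chemotherapy and antiretroviral rows at 24 hours rests partly on clinical judgement that those treatments should not be delayed. The documents do not state that reason.

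Third, eligibility narrows the exposed group. Exclusions 8 and 21 remove subjects who need prohibited drugs or cannot stop contraindicated ones, and exclusion 11 removes unstable arrhythmia. The summary of changes shows that enrollment had already begun, so a late amendment reaches fewer people. Both points limit the benefit, but neither supplies a wait.

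**Conclusion.** The point holds as a minor subject-safety improvement. For the six drugs and the CYP3A4 statins the permitted start is 6 days inside the plan's stated washout. For ergots it is 5 days inside. No provision sets a longer wait or bars use in that interval.

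The conclusion rests on reading footnote a as written and on taking the plan's own 7 days as the best available measure of how long study drug persists. It has limits. CYP3A4 inhibition is stated for POS only; for voriconazole the plan names just the enzymes that metabolize it. Table 2 gives no mechanism for ergots, which are included because concurrent use is barred and 2 days is shorter than the washout. The lack of a scheduled visit applies only to subjects who finish on Day 84 and have their end-of-therapy visit then. A reader might go further and infer demonstrated harm or a bias in the mortality comparison. The documents support neither: they give no residual concentrations and no count of affected subjects, and nothing here bears on the primary analysis.

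**What to change.** Add one sentence to footnote a: 'After study drug has been permanently stopped, wait the longer of the time in this table and 7 days before starting any drug in the life-threatening-interaction row, an ergot alkaloid or a CYP3A4-metabolized statin.'

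Astemizole then stays at 10 days. Leave all other rows, every wait before study drug starts, footnotes b and d, and the sponsor-approved deviation route unchanged.

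The cost to a subject is up to 6 more days without the listed drug, with urgent need handled by the existing deviation route. Antifungal treatment is not interrupted, because the wait begins only after study drug has permanently stopped. No new data are collected. The change still needs IRB/IEC approval (Section 9.1.1) across up to 155 centers, so it should go into the next amendment and does not justify one of its own.

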7.3.2 Subject Exclusion Criteria

A subject meeting any of the exclusion criteria listed below must be excluded from participating in the trial:

1. The subject has chronic (>1-month duration) IA, relapsed/recurrent IA, or refractory IA which has not responded to prior antifungal therapy.
2. The subject has pulmonary sarcoidosis, aspergilloma, or allergic bronchopulmonary aspergillosis (ABPA).
3. The subject has a known mixed invasive mold fungal infection including *Zygomycetes*, and/or a known invasive *Aspergillus* fungal infection in which either study drug may not be considered active.
4. The subject has received any systemic (oral, intravenous, or inhaled) antifungal therapy for this infection episode for 4 or more consecutive days (≥ 96 hours) immediately prior to randomization.
5. The subject has developed the current episode of IA infection (possible, probable, or proven infection) during the receipt of more than 13 days of an azole or polyene antifungal agent given for prophylaxis that is considered to be a mold-active, antifungal agent (including itraconazole, posaconazole, voriconazole, isavuconazole, inhaled or systemic amphotericin or lipid-associated amphotericin), Any duration of echinocandin antifungal use is allowed (prior to randomization).
6. The subject has received POS or VOR as empirical treatment for this infection for 4 days (96 hours) or more within the 15 days immediately prior to randomization.
7. The subject has received any treatment specifically listed in **Table 2** which is more recent than the indicated washout period prior to randomization.

Table 2 Prohibited Medications Prior to Start of Study Treatment and During Study Treatment

Prohibited Medications Prior to Start of Study Treatment and During Study Treatment	Washout Period^a
Systemic antifungal therapy (oral, intravenous or inhaled) for > 3 consecutive days (≥ 96 hours) for treatment of this infection.	Not eligible to participate in the study
Systemic antifungal therapy (oral, intravenous or inhaled) for ≤ 3 consecutive days (<96 hours) for treatment of this infection.	Discontinue at Randomization
Investigational drugs (new chemical or biological entities): Investigational use of approved products or chemotherapy regimens may be permitted with the approval of the sponsor's project physician prior to use.	30 days ^c

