^e Medications that are known to result in a false positive galactomannan EIA result can be used on study, but when used do not allow for galactomannan to contribute to a confirmatory probable IA diagnosis. Please refer to figure 2.1 for additional details.

HMG-CoA=beta-hydroxy-beta-methylglutaryl-CoA; IFI = invasive fungal infection

8. A subject must not have any condition that, in the opinion of the investigator, may interfere with optimal participation in the study, i.e., any condition requiring the use of prohibited drugs or unstable medical conditions other than the hematological disorder such as cardiac or neurologic disorder or impairment expected to be unstable or progressive during the course of this study (e.g., seizures or demyelinating syndromes, acute myocardial infarction within 3 months of study entry, myocardial ischemia, or unstable congestive heart failure, unstable arrhythmias, atrial fibrillation with ventricular rate <60/min, or history of torsades de pointes, symptomatic ventricular or sustained arrhythmias, unstable electrolyte abnormalities [e.g., ≥Grade 2 hypokalemia or hypomagnesemia]).
9. The subject has known hypersensitivity or other serious adverse reaction to any azole antifungal therapy, or to any other ingredient of the study medication used.

10. The female subject is pregnant, intends to become pregnant, or is nursing at the time of randomization.
11. The subject has any known history of Torsade de Pointes, unstable cardiac arrhythmia or proarrhythmic conditions, or a history of recent myocardial infarction within 90 days of study entry.
12. The subject has QTc (either Fridericia or Bazett's correction) interval \geq 500 msec on electrocardiogram performed at screening or baseline.
13. The subject has significant liver dysfunction (defined as total bilirubin $>$ 1.5 times upper limit of normal AND AST or ALT $>$ 3 times upper limit of normal with normal alkaline phosphatase [ALP] on screening labs) at the time of randomization.
14. The subject has hepatic cirrhosis or a Child-Pugh score of C (severe hepatic impairment) at the time of randomization. See [Appendix 4](#) for Child-Pugh Classification.
15. The subject has severe renal insufficiency (estimated creatinine clearance $<$ 20 mL/min) or on hemodialysis at the time of randomization or is likely to require dialysis during the study.
16. The subject has a known hereditary problem of galactose intolerance, Lapp lactase deficiency, or glucose-galactose malabsorption.

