7.4.1.3 Selection and Timing of Dose for Each Subject

7.4.1.3.1 Selecting the Dose for Each Subject

The rationale for the selection of doses to be used in this trial is presented in [Section 5.3](#). Dosing for all of the subjects will be based on [Table 3](#). The VOR IV dose will be calculated based on the screening weight of the subject. Details of the calculations can be found in the Pharmacy Manual.

Most subjects will begin antifungal azole (VOR or POS) therapy via the IV route. Azole therapy will be switched from IV route to the oral route when the subject is considered clinically stable and able to take oral medication. If during the course of the study, the subject can no longer tolerate oral medication, the subject may be switched back to IV therapy. Subjects with worsening clinical symptoms may also be switched back to IV therapy as clinically indicated. Based upon product labeling, similar study drug exposures for a 300 mg dose have been noted for POS IV and POS tablet, while 4 mg/kg IV VOR dosing achieves exposures similar to a 300 mg oral maintenance dose of VOR. Please refer to VOR EU product circular for full details [32].

If clinically indicated, some subjects may initiate study therapy via the oral route: Day 1 dosing of oral therapy is: POS 300 mg BID or VOR 300 mg BID.

For subjects with mild to moderate hepatic cirrhosis (Child-Pugh score of A or B), the standard loading dose will be used, but the maintenance dose will be reduced. See [Appendix 4](#) for Child-Pugh Classification. Appropriate dosing modifications will be included in the trial design in a blinded fashion.

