If clinically indicated, some subjects may initiate study therapy via the oral route. For these subjects POS tablet will be administered on Day 1 as a 300 mg dose BID (three 100 mg tablets, twice a day at approximately 12-hour intervals). After Day 1, the dose will be 300 mg QD (three 100 mg tablets, once a day).

If a subject vomits within 15 minutes of POS tablet administration, the dosing should be repeated as soon as possible, following appropriate antiemetic treatment. The adverse event, supportive treatments, and ability to subsequently dose study medication should be appropriately recorded in the subject's eCRF. If repeated vomiting occurs, the subject should switch to POS IV therapy.

Details of the patient's food intake surrounding each dose of POS tablet or dummy placebo tablet should be recorded relative to each dose of POS tablet. Specifically, food intake data to be recorded should include whether the subject had no food, a light meal, a moderate meal or a full meal within 2 hours before or within 1 hour after taking study drug.

The exact time of POS study drug taken prior to collection of the population PK sample, as well as the exact time the Population PK sample blood draw occurs will be recorded in the appropriate eCRF.

7.4.1.3.2.2 Voriconazole

Table 6 provides what subjects randomized to the VOR arm will receive when on IV therapy.

Table 6 Summary of VOR IV Therapy

	Day 1 Dose	Day 2-84 Dose	Day 2-84 Dose for subjects with hepatic impairment^a
Drug	VOR 6 mg/kg twice a day	VOR 4 mg/kg twice a day	VOR 2 mg/kg twice a day
Volume	200 mL	150 mL	150 mL
Infusion rate	100 mL/hr	100 mL/hr	100 mL/hr
Infusion Duration	2 hr	1.5 hr	1.5 hr

^a The maintenance dose of VOR should be reduced for subjects with mild to moderate hepatic impairment (Child-Pugh Class A and B).

Table 7 provides what subjects randomized to the VOR arm will receive when on oral therapy.

Table 7 Summary of VOR Capsule Therapy

	Daily Oral Dose 200mg BID^a	Daily Oral Dose for subjects with hepatic impairment^b 100mg BID
First Dose	2 orange VOR capsules 3 yellow POS tablet placebos	1 orange VOR capsules 3 yellow POS tablet placebos
Second Dose	2 orange VOR capsules	1 orange VOR capsules

^a If the subject starts on Day 1 with VOR Solid Oral, they will receive 300 mg BID. The first dose should be: 3 orange VOR capsules, and 3 yellow POS tablet placebos. The second dose should be: 3 orange VOR capsules, and 3 yellow POS tablet placebos.

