7.4.1.4 Blinding Trial Treatments

Double-Blind, Double-Dummy (for Oral Administration)

Only the investigational pharmacists or qualified medical personnel responsible for preparing the study drug will have knowledge of the treatment identity and will prepare study medications according to the protocol guidelines; all other study personnel will be blinded to study treatment. The unblinded pharmacists will not be involved in any post-treatment assessments for the subjects enrolled in this trial. Subjects will receive the blinded IV study therapy from the unblinded pharmacist. In order to maintain the blind, preparation of the intravenous study drugs must be performed by someone other than the persons who will evaluate the subject for clinical response and presence of adverse experiences.

IV infusions will be masked to blind the appearance of the IV study drugs. Matching placebo infusions of 5% dextrose will be used for the additional daily doses to make the number of infusions per day (2) similar in both treatment arms. Subjects in both treatment arms will receive the same number of infusions per day with equivalent infusion rates and volumes. This is not dependent on the treatment arm.

POS tablets and VOR capsules will be administered using a double-dummy, double-blind method to blind study personnel and subjects as to the assigned treatment arm. Oral VOR will be given as over-encapsulated tablets with each capsule

containing 100 mg of VOR or a placebo to VOR. The POS oral tablet will also be blinded by use of a dummy tablet with each tablet containing 100 mg of POS or a placebo to POS. Subjects in both treatment arms will receive the same number of tablets and capsules per day when on oral therapy. This is not dependent on the treatment arm.

As VOR labeling recommends, dosage adjustment based upon hepatic insufficiency will be made. The maintenance dose of VOR will be reduced in subjects with mild to moderate hepatic impairment (Child-Pugh Class A and B). Subjects on VOR IV will receive 2 mg/kg maintenance dose BID. Subjects on VOR capsules will receive 100 mg BID. Appropriate dosing modifications will be included in the trial design in a blinded fashion. There is no planned dose reduction or dose adjustment of POS IV or POS tablet or POS dummy tablet.

This study will be conducted using in-house blinding procedures. See [Section 7.7.2.6.4](#) for a description of the method of unblinding a subject during the trial, should such action be warranted.

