7.7.2.6.3 Modification of Dose and/or Administration of Investigational Product for a Subject

For subjects with mild to moderate hepatic cirrhosis (Child-Pugh Class A and B) may be enrolled in the study; however, the dose of VOR IV and capsules will need to be adjusted. The dose on Day 1 will be as described, but the dose thereafter will be reduced. Appropriate dosing modifications will be included in the trial design in a blinded fashion. There is no planned dose reduction or dose adjustment of POS IV or POS oral tablet or POS dummy tablet.

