Appendix 4 Child-Pugh Scoring and Classification

Child-Pugh Scoring

Measure	1 point	2 points	3 points
Total bilirubin, μmol (mg/dl)	<34 (≤ 2)	34-50 (2-3)	>50 (>3)
Serum albumin, g/dl	>3.5	2.8-3.5	<2.8
PT prologation (INR)	<4 seconds (<1.7)	4-6 seconds (1.71-2.30)	>6 seconds (>2.30)
Ascites	None	Mild	Moderate to Severe
Hepatic encephalopathy	None	Grade I-II (or suppressed with medication)	Grade III-IV (or refractory)

Child-Pugh Interpretation

Points	Class
6	A
7-9	B
10-15	C

NOTE: Patients with IA will often have low albumin scores due to their underlying conditions or the fungal infection itself. Hence, a patient who meets the criteria for Child-Pugh Class A or B based solely on a low albumin score without any other measure of hepatic insufficiency (i.e., albumin 2 or 3 points but no other hepatic measure above 1 point) should not be considered to have mild or moderate hepatic insufficiency, and, thus, such patients do not truly meet the mild or moderate hepatic insufficiency criterion to reduce the VOR dose.

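### Exclusion criterion 14 bars all hepatic cirrhosis, while Section 7.7.2.6.3 allows Child-Pugh A and B cirrhosis to be enrolled and Section 7.4.1.3.1 gives it a dosing rule

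*Combined protocol and SAP*

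**What the plan says.** Four places in the protocol bear directly on the point.

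- **Section 7.3.2, exclusion 14**, repeated word for word as item 14 of the key exclusion criteria in the synopsis: "The subject has hepatic cirrhosis or a Child-Pugh score of C (severe hepatic impairment) at the time of randomization".
- **Section 7.3.2, opening sentence**, which gives the list its force: "A subject meeting any of the exclusion criteria listed below must be excluded from participating in the trial".
- **Section 7.7.2.6.3**, on dose modification: subjects with "mild to moderate hepatic cirrhosis (Child-Pugh Class A and B) may be enrolled in the study", with an adjustment to the voriconazole dose.
- **Section 7.4.1.3.1**, on dose selection: "For subjects with mild to moderate hepatic cirrhosis (Child-Pugh score of A or B), the standard loading dose will be used", after which the maintenance dose is reduced.

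Other passages concern the same dose modification but use a different term. Section 7.4.1.4 states: "The maintenance dose of VOR will be reduced in subjects with mild to moderate hepatic impairment (Child-Pugh Class A and B". The footnotes to Tables 6 and 7 are worded almost the same way, and Tables 4 and 5 have a column for subjects with hepatic impairment. None of these passages mentions cirrhosis.

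**The concern.** The exclusion list and the dose-modification section give opposite answers to one eligibility question: may a patient with Child-Pugh A or B cirrhosis enter the trial?

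Two things depend on the answer. The first is conduct. With up to 155 centers planned, a site working from Section 7.3.2 would turn such a patient away, and a site working from Section 7.7.2.6.3 could enroll the patient and give study drug. The second is data review. The synopsis and Section 8.1 require protocol violators to be identified before unblinding, but for these subjects the reviewers have no single rule. Hepatic safety is a Tier 1 endpoint (Sections 8.3.2 and 8.5.2), so it should be clear which patients with liver disease the trial meant to admit.

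**Working it through.** No arithmetic applies. The claim rests on no rate, margin, power or sample size, and the plan gives no figure to reproduce. The check sets the passages side by side for each type of candidate.

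| Candidate at randomization | Exclusion 14 | Sections 7.7.2.6.3 and 7.4.1.3.1 | Tables 4 to 7, Section 7.4.1.4 | Conflict? |
|---|---|---|---|---|
| Cirrhosis, Child-Pugh A or B | Excluded (first limb) | May be enrolled; dosing rule given | Cover Child-Pugh A/B impairment | **Yes** |
| Cirrhosis, Child-Pugh C | Excluded (both limbs) | Not admitted | No class C rule | No |
| No cirrhosis, Child-Pugh A or B impairment | Neither limb met | Not mentioned | Dose modification given | No |
| No cirrhosis, Child-Pugh C | Excluded (second limb) | Not admitted | No class C rule | No |

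Only the first row fails. There the exclusion is mandatory under the opening sentence of Section 7.3.2, while Section 7.7.2.6.3 gives permission to enroll.

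**The two opposing sections carry different weight.** Section 7.7.2.6.3 is the only place that says these subjects may be enrolled. Section 7.4.1.3.1 says nothing about enrollment. It conflicts by implication, because it gives a rule for subjects whom exclusion 14 would keep out at entry.

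**Four readings that might remove the conflict:**

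1. *The dosing text covers only cirrhosis that arises after randomization.* This does not fit Section 7.7.2.6.3, which speaks of enrolling such subjects.
2. *Exclusion 14 means cirrhosis of class C only.* This may have been the intent, but the criterion joins cirrhosis and class C by *or*, and nothing limits the first limb.
3. *Sections 7.7.2.6.3 and 7.4.1.3.1 mean impairment without cirrhosis.* This may also have been the intent, since Section 7.4.1.4 and the footnotes to Tables 6 and 7 describe the same dose modification in terms of impairment. But both sections use the word cirrhosis.
4. *Appendix 4 settles it.* Its note concerns only subjects who reach class A or B through low albumin alone, and says that "such patients do not truly meet the mild or moderate hepatic insufficiency criterion to reduce the VOR dose". It addresses neither cirrhosis nor exclusion 14.

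**Reach into the analysis.** Any such subject who is randomized and dosed enters the ITT population (Section 8.4.1) and the APaT population (Section 8.4.2). Section 8.4 defines no per-protocol set, so being classed as a violator would not remove the subject from either. The contradiction therefore affects who is admitted and how deviations are counted. It does not change how an admitted subject is analyzed.

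**The case against.** The best defense is that eligibility already has a governing list. Section 7.3.2 is mandatory, the synopsis repeats it, and Section 7.6 requires eligibility to be confirmed before randomization. The opposing sentence is grammatically broken and sits in a dose-modification section that a site would not normally consult to decide eligibility. This makes divergent practice less likely. It does not remove the contradiction, because no text says that the list overrides Section 7.7.2.6.3, and a site that relied on that section would be following current protocol wording.

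Two stronger conclusions are tempting, and the documents support neither.

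- *A reader might infer that the hepatic safety comparison, or the comparison of posaconazole with voriconazole in general, is biased*, particularly since the hepatic dose modification applies to voriconazole only. But eligibility is settled before assignment, randomization is 1:1 within risk strata, and treatment is double-blind (Sections 7.4.1.2 and 7.4.1.4). Inconsistent admission can change the case mix and the deviation count. Nothing in the documents shows that it favors an arm.
- *A reader might infer that all the hepatic dosing text is void under exclusion 14.* It is not. Tables 4 to 7 and Section 7.4.1.4 refer to hepatic impairment. A subject with Child-Pugh A or B impairment and no cirrhosis meets neither limb of exclusion 14, so those passages can stand beside it.

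**Conclusion.** The contradiction is real and should be corrected. For a candidate with Child-Pugh A or B cirrhosis at randomization, exclusion 14 and Section 7.7.2.6.3 cannot both be followed, and Section 7.4.1.3.1 presupposes the enrollment that exclusion 14 forbids. Eligibility, violator status and the makeup of the ITT and APaT populations are unsettled for that group and for no other.

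The size cannot be computed, because the documents give no count of cirrhotic candidates or enrolled subjects. That sites have in fact acted differently is a possibility that the text leaves open, not something it shows. No effect on the primary endpoint, the power or the 10% margin is claimed. The conclusion rests on the literal wording of current text. Whichever meaning was intended, at least one of these places must be reworded to say it.

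**What to change.** Reconcile exclusion 14 (synopsis and Section 7.3.2) with Sections 7.7.2.6.3 and 7.4.1.3.1, so that one statement says whether a subject with Child-Pugh A or B cirrhosis at randomization is eligible, and bring the other places into line with it. Which rule is right is for the sponsor's clinical team to decide. In the same pass, align the use of *cirrhosis* and *hepatic impairment* across Section 7.4.1.3.1, Section 7.7.2.6.3, Tables 4 to 7 and Section 7.4.1.4. For the tables and Section 7.4.1.4 this concerns terminology only.

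The cost is more than a wording change. An amendment needs IRB/IEC approval (Section 9.1.1). The summary of changes refers to subjects already enrolled, so recruitment has begun. New wording will not settle the status of any subject with Child-Pugh A or B cirrhosis admitted before it. Those subjects need a blinded deviation review under the agreed rule before database unblinding, and reporting their number by arm after unblinding would show how far the inconsistency reached.
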